5.11 Sample Size Justification

The primary sample size calculation was based on the ability to detect a moderate correlation ($r=0.5$) between serum and urine levels. With 40 patients, there will be 90% power to detect moderate correlations based on a two-sided test of the Fisher's Z test of the Pearson correlation (Image 1). Power calculations were performed using SAS software (version 9.4; Cary, NC). (8)

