5.3 Overall Study Design

This is a prospective specimen collection cohort study to evaluate the correlation between serum and urine values of the bone marker of interest, and their association with baseline DEXA scan measures and fracture risk within 6 months.

Study samples will be obtained longitudinally. One collection of both serum and urine collection will be obtained. The urine will be collected as second void of day and at the same time the blood collection is drawn. Study will continue for a period or 1 year, with plan to enroll around 40 subjects.

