5.5 Inclusion and Exclusion Criteria

Subject Inclusion criteria

- Consent to participate in the study
- Participants limited to subjects in the CCF
- Age between and inclusive of 18 and 85 years of age
- No gender exclusion
- Patients diagnosed with Osteopenia on DEXA scan who have not been on any medical therapy in the past
- Presence of normal vitamin D levels, kidney function, and parathyroid hormone levels (per our reference ranges)

Sample Inclusion Criteria

- Serum sample collected in Serum Separator Tubes (SST) Gold tube and urine sample collected in clean container
- Samples to be collected only at a CCF Laboratory based on standard of care for the CCF
- Samples to be collected at the same time of day. Urine NTX will be collected as the second void of the day

Subject Exclusion criteria

- Prior history of medical therapy for osteopenia
- Prior radiation therapy
- Prior history of bone fracture
- History of high risk medication associated with increased risk of fracture
- Presence of abnormal vitamin D levels, kidney function, and parathyroid hormone
- Pregnancy status (verbal)
- Those with medical co-morbidities that increase the risk of fracture will be excluded and these include but are not limited to: rheumatoid arthritis, ankylosing spondylitis, psoriatic arthritis, diabetes mellitus, hyperparathyroidism, chronic kidney disease, pituitary disease, multiple myeloma, leukemia, lymphoma, thalassemia major, HIV/AIDS, malabsorption, Inflammatory bowel disease, chronic obstructive pulmonary disease, hypogonadism, chronic liver disease, untreated hyperthyroidism, and those with chronic immobility

Sample Exclusion Criteria

- Grossly hemolyzed (red) or turbid samples
- Samples with visually detected microbial contamination
- Sample not handled or stored as per sample handling instructions, which will be provided to the study sites at the time of the study initiation visit
- Urine sample that is not collected as second void of the day

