5.10 Statistical Analyses

Pearson or Spearman correlations will be used to measure the association between serum and urine markers. Similar correlation measures will be used to measure associations with DEXA scan results, and Comparisons of the correlations were performed using the cocor package in R software (version 4.0;

Vienna, Austria) using the methods by Meng, Rosenthal, and Rubin (1992) to compare the correlations and calculate 95% confidence intervals for their difference. As an exploratory analysis, associations between serum and urine levels with fracture risk will be evaluated using two-sample t-tests and, if feasible, ROC analyses will be used to compare the predictive ability of each marker. If the number of fractures is small, this analysis will not be performed. If the follow-up through 6 months cannot be measured consistently across patients, alternate methods including time to event analysis may be used to account for differential follow-up.

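### Does leaving Pearson or Spearman open, with no allowance for unusable samples, undermine the stated 90% power?

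*Combined protocol and SAP*

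**What the plan says.** Section 5.11 bases the sample size on the "ability to detect a moderate correlation ($r=0.5$) between serum and urine levels", using a "two-sided test of the Fisher's Z test of the Pearson correlation", and concludes: "With 40 patients, there will be 90% power to detect moderate correlations". It refers to an image for the calculation, which is not visible in the text available here. Section 5.3 describes the study "with plan to enroll around 40 subjects".

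Section 5.10 gives the analysis: "Pearson or Spearman correlations will be used to measure the association between serum and urine markers". It names no rule for choosing, no measurement scale and no significance level for this test. The only confidence level given is for another quantity, the comparison of correlations, where the plan will "calculate 95% confidence intervals for their difference".

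Section 5.5 excludes samples on quality, handling and timing grounds, for example "Grossly hemolyzed (red) or turbid samples" and "Urine sample that is not collected as second void of the day". No expected loss rate or replacement rule is given.

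**The concern.** The serum-urine correlation is the study's objective and the only analysis with a power calculation, yet the powered test is only one of two that section 5.10 allows. Spearman is somewhat less efficient on normal data. Pearson on an untransformed, right-skewed marker can lose more. A pair is lost when either specimen is rejected, so 40 enrolled may mean fewer than 40 analysed. If the coefficient were picked after seeing both results, there would be two chances of significance.

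On that reading, the study would have roughly 83% to 88% power instead of 90%, with a false-positive rate above 5%.

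**Working it through.** **Inputs.** From section 5.11: n = 40, r = 0.5, two-sided Fisher z test. Assumed because not stated: null correlation 0 and significance level 0.05. The documents give no loss rate and no distribution for the marker, so values for these below are illustrations.

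**1. The plan's own figure.** Power = Φ(atanh(r)·√(n−3) − 1.96), with atanh(0.5) = 0.5493.

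- n = 40: 0.5493 × √37 = 3.341; 3.341 − 1.960 = 1.381; Φ = 91.6%.
- Adding the bias term r/(2(n−1)) = 0.5/78 = 0.0064: 0.5557 × 6.083 = 3.380; 3.380 − 1.960 = 1.420; Φ = 92.2%.

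The stated 90% is reproduced, with a little to spare.

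**2. Lost pairs, Pearson.**

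| Usable pairs | Plain Fisher z | With bias term |
|---|---|---|
| 40 | 91.6% | 92.2% |
| 38 | 90.1% | 90.8% |
| 37 | 89.3% | 90.0% |
| 36 | 88.4% | 89.2% |
| 34 | 86.4% | 87.3% |

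Power drops below 90% at the third lost pair by the plain formula and at the fourth with the bias term. At 36 pairs (10% loss, assumed) the shortfall is 1 to 2 points.

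Precision barely moves. For an observed r of 0.5, the 95% interval is tanh(0.549 ± 1.96/√37) = 0.22 to 0.70 with 40 pairs, and tanh(0.549 ± 1.96/√33) = 0.21 to 0.71 with 36.

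**3. Spearman.** The answer depends on which coefficient equals 0.5.

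- If the underlying bivariate normal correlation is 0.5, then ρs = (6/π)·asin(0.25) = 0.483. With variance 1.06/(n−3), power at 40 is Φ(0.5264 × √(37/1.06) − 1.96) = Φ(1.150) = 87.5%. The larger variance (1 + ρs²/2)/(n−3) gives 85.8%, and simulation (100,000 replicates) gives 88.6%. At 36 pairs the three figures are 83.6%, 81.6% and 84.9%.
- If the Spearman coefficient itself is 0.5, power at 40 is Φ(0.5493 × 5.908 − 1.96) = Φ(1.285) = 90.1%, and 90.9% by simulation.

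**4. Skewed data.** Take lognormal markers with log-scale correlation 0.5 and assumed log-SD 0.3, 0.5, 0.7 or 1.0. Raw-scale Pearson at n = 40 then has power 90%, 86%, 79% or 67%. Part of that fall is a smaller target, because the raw-scale correlation is then only 0.489, 0.469, 0.439 or 0.378. Spearman depends only on ranks, so skewness leaves its power unchanged at the figures in step 3. Choosing by a Shapiro-Wilk check (10,000 replicates, n = 40) gave 91.7% on normal data, 88.2% at log-SD 0.5 and 88.9% at log-SD 0.7.

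**5. Type I error at n = 40, by simulation.**

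| How the coefficient is chosen | Type I error |
|---|---|
| Pearson alone | 5.0% |
| Spearman alone | 5.1% |
| By Shapiro-Wilk check | 4.9% to 5.0% |
| Better p-value of the two, normal data | 6.6% |
| Better p-value of raw Pearson and Spearman, skewed data | 7.1% to 9.3% |

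Reporting the better p-value also raises power, to about 93% at 40 pairs. Reduced power and inflated error therefore belong to different behaviours and do not occur together.

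**The case for a change.** The best case for acting is that the one powered analysis is not uniquely defined and that defining it would cost a sentence. Spearman, which the plan permits, can miss 90% with no loss at all. Section 5.1 itself describes second-void collection as potentially cumbersome, so some lost pairs are plausible. With Spearman and 36 pairs, power could be 82% to 85%. Nothing in section 5.10 forbids choosing on the result.

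Much of this is true as description. The selection rule and the loss allowance are unstated, and a planner who wanted 90% under Spearman with a normal-scale correlation of 0.5 would need about 44 usable pairs. The consequences, however, are conditional. The low eighties require both Spearman and a loss rate that the documents do not supply. Heavy losses from skewness require an analyst to keep raw-scale Pearson on visibly skewed data although the plan offers a rank-based alternative. Inflated error requires selection by p-value, which silence about a rule does not amount to. Prescribing a log scale would rest on a distribution that the documents do not describe. The image cited in section 5.11 may also show power at other sample sizes, so that detail cannot be called absent.

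**Conclusion.** No change follows. The stated power is correct for the test, effect and number of pairs to which section 5.11 ties it. Using Spearman costs about 3 to 6 points at most with 40 pairs, and nothing relative to the stated 90% if 0.5 is read as the Spearman coefficient. Losing 10% of pairs costs Pearson about 3 points from its actual 91.6% to 92.2%.

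Naming both coefficients without a rule is a gap that analysts usually fill by looking at the distributions, and that practice held the error rate at about 5% in the check above. The phrase "with plan to enroll around 40 subjects" states an approximate target, so it does not rule out enrolling a few more if samples are rejected.

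These conclusions assume a two-sided 5% level, a null correlation of zero, and a coefficient not chosen by its p-value. If it were chosen that way, the result should be read with an error rate of about 7% to 9%.

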6.0 DATA MANAGEMENT

The Principal Investigator (PI) is responsible for ensuring that all data are submitted in a timely fashion.

6.1 Data Management

We will use RedCap database, only CCF MRN as identifier, assign serial number to each unique patient and store data on a Cleveland Clinic Shared Drive which will be accessed on workstations requiring login credentials. Once data are collected, we will de-identify the rows and use only serial numbers.

6.2 Data Clarification

During the conduct of the study, if a question regarding the data arises, the Monitor and/or Delegate will work with the site to resolve the issue. All communications will be documented in a query via the electronic database.

7.0 ADVERSE EVENT REPORTING

Unanticipated Non-Serious Adverse Event Reporting:

Unanticipated non-serious adverse events assessed by the PI as being either caused by, or related to, the study procedures, will also be reported using the Adverse Event Report form.

The following adverse events are anticipated as a result of the blood collection required per the study procedures: pain, bruising, bleeding or infection at the site where the blood was collected from the subject. Fainting may also occur as a result of blood collection. Because these events are anticipated, they do NOT need to be reported using the Adverse Event Report form as long as they are not assessed as serious. If assessed as serious, then they need to be reported.

7.1 Date of Awareness

A test site becomes aware of an MDR reportable event when medical personnel who are employed by or otherwise formally affiliated with the facility acquire information that reasonably suggests that a reportable event has occurred. Medical personnel include persons who are licensed, registered, or certified to administer healthcare, who have received a diploma or a degree in a professional or scientific discipline, or who are responsible for receiving medical complaints or adverse event reports or who supervise such persons.

8.0 ADMINISTRATION

8.1 Ethics Committee or Institutional Review Board Review

It is the responsibility of the Investigator to provide the Study Monitor or designee with written documentation demonstrating that this study has been approved by the Institutional Review Board (IRB)/Independent Ethics Committee (IEC). A copy of the signed documentation must be returned to the study monitor or designee.

8.2 Investigator Delegation of Responsibilities

The Investigator's decision to delegate study related responsibilities to his study personnel will be recorded on the *Principal Investigator Delegation of Responsibilities and Signature Log*.

8.3 Disposition of Data

All data and information obtained during this evaluation are the property of CCF and may be used in support of regulatory submissions.

8.4 Record Retention

The Principal Investigator will ensure that study records are maintained in accordance with IRB/IEC

At a minimum the following documentation will be maintained:

- All correspondence with the IRB/IEC, study monitor or designee, including required reports
- The protocol and regulatory documentation
- Copies of all data

8.5 Protocol Amendments

Amendments to this protocol will be signed by the Investigator, and approved or exempted by IRB/IEC as required, prior to implementation.

8.6 Deviations from the Agreed Protocol

Deviations from the written protocol should be avoided. If deviations occur, they must be reported immediately to the Study Monitor or designee and recorded in a Protocol Deviation Memorandum.

